8.3.3.3 EXPECTEDNESS

The PI and co-investigator team will be responsible for determining whether an adverse event (AE) is expected or unexpected. An AE will be considered unexpected if the nature, severity, or frequency of the event is not consistent with the risk information previously described for the study intervention (i.e. the package insert approved in Japan).

8.3.4 TIME PERIOD AND FREQUENCY FOR EVENT ASSESSMENT AND FOLLOW-UP

The occurrence of an adverse event (AE) or serious adverse event (SAE) may come to the attention of study personnel during study visits and interviews of a study participant presenting for medical care, or upon review by a study monitor.

All AEs including local and systemic reactions not meeting the criteria for SAEs will be captured on the appropriate case report form (CRF). Information to be collected includes event description, time of onset, clinician's assessment of severity, relationship to study product (assessed only by those with the training and authority to make a diagnosis), and time of resolution/stabilization of the event. All AEs occurring while on study must be documented appropriately regardless of relationship. All AEs will be followed to adequate resolution.

Any medical condition that is present at the time that the participant is screened will be considered as baseline and not reported as an AE. However, if the study participant's condition deteriorates at any time during the study, it will be recorded as an AE.

Changes in the severity of an AE will be documented to allow an assessment of the duration of the event at each level of severity to be performed. AEs characterized as intermittent require documentation of onset and duration of each episode.

Study personnel will record all reportable events with start dates occurring any time after informed consent is obtained until 7 (for non-serious AEs) or 30 days (for SAEs) after the last day of study participation. At each study visit, the investigator will inquire about the occurrence of AE/SAEs since the last visit. Events will be followed for outcome information until resolution or stabilization.

8.3.5 ADVERSE EVENT REPORTING

An external DSMB will be appointed to oversee this study, to assess safety and to determine early evidence of efficacy or futility at a planned interim data examination. The PI and co-investigators will record all adverse events and report them to the sponsor according to the timetable for reporting specified in the protocol.

All AEs will be reported to regulatory authorities, IRB, and investigators in accordance with all local applicable laws and regulations.

8.3.6 SERIOUS ADVERSE EVENT REPORTING

The study clinician(s) will report to the Sponsor-Investigator within 24 hours of awareness of the event, any serious adverse event, whether or not considered study intervention related, including those listed in the protocol or package insert and must include an assessment of whether there is a reasonable possibility that the study intervention caused the event. Study endpoints that are serious adverse events (e.g., all-cause mortality) must be reported in accordance with the protocol unless there is evidence suggesting a causal relationship between the study intervention and the event (e.g., death from anaphylaxis). In that case, the investigator must immediately report the event to the sponsor.

All serious adverse events (SAEs) will be followed until satisfactory resolution or until the site investigator deems the event to be chronic or the participant is stable. Other supporting documentation of the event may be requested by the study sponsor and should be provided as soon as possible.

The Sponsor-Investigator will be responsible for notifying the Food and Drug Administration (FDA) of any unexpected fatal or life-threatening suspected adverse reaction as soon as possible, but in no case later than 7 calendar days after the sponsor's initial receipt of the information and within 15 days for all other serious unexpected suspected adverse reactions (SUSARs), in an Investigational New Drug (IND) safety report.

8.3.7 REPORTING EVENTS TO PARTICIPANTS

Not applicable

8.3.8 EVENTS OF SPECIAL INTEREST

Not applicable

8.3.9 REPORTING OF PREGNANCY

Given that the duration of study drug administration is one week, a new pregnancy is unlikely to be reported. If so, the participant so reporting a new pregnancy will be stopped from receiving study drug/placebo. Other followup may be continued.

8.4 UNANTICIPATED PROBLEMS

8.4.1 DEFINITION OF UNANTICIPATED PROBLEMS (UP)

The Office for Human Research Protections (OHRP) considers unanticipated problems involving risks to participants or others to include, in general, any incident, experience, or outcome that meets all of the following criteria:

- Unexpected in terms of nature, severity, or frequency given (a) the research procedures that are described in the protocol-related documents, such as the Institutional Review Board (IRB)-approved research protocol and informed consent document; and (b) the characteristics of the participant population being studied;
- Related or possibly related to participation in the research (“possibly related” means there is a reasonable possibility that the incident, experience, or outcome may have been caused by the procedures involved in the research); and
- Suggests that the research places participants or others at a greater risk of harm (including physical, psychological, economic, or social harm) than was previously known or recognized.

8.4.2 UNANTICIPATED PROBLEM REPORTING

The investigator will report unanticipated problems (UPs) to the reviewing Institutional Review Board (IRB) and to the lead principal investigator (PI). The UP report will include the following information:

- Protocol identifying information: protocol title and number, PI’s name, and the IRB project number;
- A detailed description of the event, incident, experience, or outcome;
- An explanation of the basis for determining that the event, incident, experience, or outcome represents an UP;
- A description of any changes to the protocol or other corrective actions that have been taken or are proposed in response to the UP.

To satisfy the requirement for prompt reporting, UPs will be reported using the following timeline:

- UPs that are serious adverse events (SAEs) will be reported to the IRB and to the DCC/study sponsor within 2 days of the investigator becoming aware of the event.
- Any other UP will be reported to the IRB and to the DCC/study sponsor within <insert timeline in accordance with policy> of the investigator becoming aware of the problem.
- All UPs should be reported to appropriate institutional officials (as required by an institution’s written reporting procedures), the supporting agency head (or designee), and the Office for Human Research Protections (OHRP) within 2 days.

8.4.3 REPORTING UNANTICIPATED PROBLEMS TO PARTICIPANTS

Not applicable to the study population.

9 STATISTICAL CONSIDERATIONS

9.1 STATISTICAL HYPOTHESES

All tests performed will be tests of superiority.

For the primary endpoint, we will test the hypothesis that camostat mesylate results in a significantly greater change from baseline to day 4 in respiratory (Nasopharyngeal swab, saliva RT-PCR) \log_{10} viral load compared to placebo.

Similarly, for secondary endpoints we will test the hypothesis that camostat mesylate will result in a significantly greater change from baseline to days 2 and 6 in respiratory (nasopharyngeal swab, saliva RT-PCR) \log_{10} viral load compared to placebo; that camostat mesylate will reduce \log_{10} of a positive COVID19 test at days 2 and 6 (optional swabs), rate of positive tests at days 6, 14 (required), and 28 (required); and that camostat mesylate will result in lower symptom burden at days 6 and 14.

9.2 SAMPLE SIZE DETERMINATION

The sample size calculation is based on the primary outcome of interest: change in \log_{10} respiratory (nasopharyngeal swab, saliva swab RT-PCR) viral load from baseline to day 4 post-randomization. Given the limited data on the variability of the change in \log_{10} viral load, we have powered the study based on detecting a moderate standardized effect size of 0.3 using an analysis of covariance (ANCOVA), adjusting for baseline \log_{10} viral load. To put into context, one scenario that would produce a 0.3 standardized effect size would be a change of 4 in \log_{10} viral load in the camostat mesylate group compared to a change of 1 in \log_{10} viral load in the placebo group assuming a standard deviation of 5.0. (NOTE: For ANCOVA, the effect size is the standard deviation of the treatment means divided by the pooled standard deviations of the observations.) To be conservative we assume a R-squared of 0 between the \log_{10} viral RNA at 4-days and baseline \log_{10} viral RNA. With a power of 90%, and a type I error rate of 10% (2-sided), we would be able to detect the hypothesized 0.3 standardized effect size with 98 total patients - 49 patients per group with a 1:1 randomization. Increasing this sample size by 15%, 5% for an efficacy and futility look at 50% information (i.e. when half of the patients have been enrolled) and 10% to account for loss to follow up, gives a total of 114 participants (57 per treatment arm).

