6.4 STUDY INTERVENTION COMPLIANCE

The study design is built around obtaining respiratory swabs and saliva from participants. To encourage compliance with study protocol, study drug/placebo will be provided every other day (prior to swabbing and saliva collection) and verbal assessment of whether study drug/placebo was taken as prescribed will be done.

Participants will have the option of not being swabbed again or providing saliva, even after receiving study drug, but lack of day 0 and 4 NP swabs would be a protocol deviation although they would be retained in intention to treat analysis. NP swabs are required at days 0, 4, 14, 28; optional swabs at days 2 and 6. Saliva will be collected at all study visits.

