9.4.2 ANALYSIS OF THE PRIMARY EFFICACY ENDPOINT(S)

The primary analysis will be according to intent-to-treat and conducted using ANCOVA, adjusting for baseline \log_{10} viral load (or conversion from Ct value assuming $1 \log_{10} = 3.3$ Ct units). We will use the t-statistic for the treatment effect to determine whether the treatment is statistically different from the placebo at the overall 10% level of significance, controlling for baseline \log_{10} viral load. Because of the interim analysis (see below), a p-value of 0.06 (2-sided), corresponding to an efficacy boundary value of 1.875 at the last look, will be used for the level of significance for the primary outcome at the final analysis. In sensitivity analyses, we will also adjust for age and time since onset of symptoms. We will also conduct a per-protocol analysis as a secondary analysis. We will assess the missing mechanism and the impact of missing data. Sensitivity analyses under either missing at random or missing not at random will be considered, as appropriate.

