9.4.6 PLANNED INTERIM ANALYSES

Interim monitoring for safety, efficacy and futility will be conducted. When 50% of the participants have accumulated the primary endpoint, we will conduct an interim analysis to assess for efficacy and futility using the group sequential method with asymmetric boundaries. We will use a Pocock boundary for efficacy and will consider stopping early for efficacy if the t-statistic for the treatment effect is greater than the critical value of 1.875; we propose stopping for futility if the drug is trending in the wrong direction, and have set a futility boundary value of -1. Safety will be assessed by comparing the rate of adverse events in the treatment group using Type I error of 5% (2-sided); no control for multiplicity will be done for safety outcomes.

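### Section 9.2 allows 5% for the interim look, but the stated Pocock boundary needs about 11%; at the plan's own 10% loss, 114 enrolled gives about 89% power rather than 90%

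*Combined protocol and SAP*

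**What the plan says.** Section 9.2 sizes the trial on the day-4 change in log10 viral load, with standardized effect size 0.3, ANCOVA, 90% power and two-sided type I error of 10%. On the covariate it says "To be conservative we assume a R-squared of 0". This gives 98 patients, 49 per group. The enlargement follows: "Increasing this sample size by 15%, 5% for an efficacy and futility look at 50% information", and then "10% to account for loss to follow up, gives a total of 114 participants (57 per treatment arm".

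The look itself is specified elsewhere. Section 9.4.6 describes one interim analysis at 50% of primary endpoints, "using the group sequential method with asymmetric boundaries". It names a Pocock boundary for efficacy, says the trial "will consider stopping early for efficacy if the t-statistic for the treatment effect is greater than the critical value of 1.875", and sets futility at -1. Section 9.4.2 carries the same constant to the end: "a p-value of 0.06 (2-sided), corresponding to an efficacy boundary value of 1.875 at the last look".

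No source is given for the 5%, and power is not restated for the two-look design or for 114.

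**The concern.** A Pocock boundary spends much of its error at the interim look and pays for it with a stricter final test: 1.875 here, against 1.645 for a fixed design at two-sided 10%. That price is a known multiple of the fixed sample size, and 5% is less than half of it.

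Two stated or implied figures are affected. One is that 114 delivers 90% power after 10% loss. The other is how much missing day-4 data the trial can absorb. Section 2.1 says the drug would not be pursued if viral load is not reduced, so the false-negative risk should be stated correctly, even though the error is small.

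**Working it through.** **Inputs.** From 9.2: f = 0.3, which for two equal arms is a standardized difference d = 2f = 0.6 (the plan's example agrees: (4 − 1)/5.0 = 0.6); two-sided alpha 0.10; power 90%; R-squared 0; N = 98; 5% and 10% allowances; total 114. From 9.4.2 and 9.4.6: critical value 1.875 at both looks, interim at information fraction 0.5, futility bound −1.

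**1. The plan's own figures.** Noncentral F with f = 0.3 gives 89.9% power at N = 96 and 90.4% at N = 98, so 98 reproduces. 98 × 1.15 = 112.7, which becomes 114 when rounded up to an even number. The total also reproduces.

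**2. Which boundary it is.** Under the null, the two test statistics have correlation √0.5. Solving 1 − P(|Z1| < c, |Z2| < c) = 0.10 gives c = 1.8754, nominal p = 0.0607. So 1.875 is the two-look Pocock constant for the plan's error rate, and there is no doubt about the design meant.

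**3. The inflation it needs.** Let θ be the expected final statistic. Then Z1 has mean θ√0.5, Z2 has mean θ, and

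power = P(Z1 > 1.875) + P(Z1 ≤ 1.875, Z2 > 1.875).

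- 90% power requires θ = 3.082.
- A fixed design requires θ = 1.645 + 1.282, or 2.926 before rounding.
- Ratio: (3.082 / 2.926)² = 1.109. Adding the futility bound of −1 leaves it at 1.109.
- For comparison, an O'Brien–Fleming boundary would need 1.4%, so 5% does not match that shape either.

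**4. Evaluable number for 90%.** With θ = d√(N/4), N = 4 × (3.082 / 0.6)² = 105.5, so about 106. Multiplying 98 by 1.109 gives 108.7, but that carries forward the surplus already in 98; the exact fixed normal size is 4 × (2.926 / 0.6)² ≈ 95.1.

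**5. Power at the numbers that matter.** R-squared 0, d = 0.6. The simulation columns give the range over separate runs of at least 100,000 trials each, with and without a covariate in the model.

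| Evaluable | Normal scale, 1.875 | Simulation, t > 1.875 | Simulation, t matched to p = 0.0607 |
|---|---|---|---|
| 102 | 89.1% | 88.9–89.1% | 88.3–88.6% |
| 103 | 89.3% | – | – |
| 106 | 90.1% | 89.7–90.1% | 89.2–89.7% |
| 108 | 90.6% | 90.3–90.6% | 89.9–90.2% |
| 114 | 91.9% | 91.5–91.9% | 91.3–91.6% |

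**6. Loss tolerated.** The plan's 10% leaves 114 × 0.9 = 102.6. To keep 106, the trial can lose 8 of 114 (7.0%); to keep 108, it can lose 6 (5.3%).

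**7. What a bare swap would imply.** Changing only 5% to 11% gives 98 × 1.21 = 118.6, or 120 when evened, which contradicts 114. Compounding gives 98 × 1.109 × 1.10 = 119.6 (also 120), and dividing by 0.9 gives 120.8 (122).

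**The case against.** The best case for leaving the text alone is that about one point of power is immaterial in a calculation built on an illustrative standard deviation and admittedly limited variability data. Three features add margin.

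- **R-squared is set to 0.** In the ANCOVA simulation at 102 evaluable, R-squared of 0.05 gives 90.1% with t > 1.875 (89.6% with matched cut-offs). The documents give no value, so 0.05 is an assumption, and 9.2 makes its 90% claim at 0.
- **Withdrawals are replaced.** Section 7.2 says treated participants who withdraw will be replaced, and 7.3 classes unreachable participants as withdrawn. If replacements come on top of 114, power stays near 92%. But 9.2 budgets 10% loss inside 114, and replacement does not cover someone who stays in the study without a day-4 sample. Section 6.4 foresees missing swabs: "lack of day 0 and 4 NP swabs would be a protocol deviation although they would be retained in intention to treat analysis". Saliva is due at every visit and the endpoint names it too, so a missing swab need not mean a missing endpoint.
- **The 90% is attached to 98.** Section 9.2 never states a power for 114. That is fair, but the allowances have no purpose except to preserve the 90%.

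All three bear on the size of the shortfall. None makes 5% the right allowance for this boundary.

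A reader might also infer that the thresholds need correcting, because 9.4.2 equates p = 0.06 with 1.875 while testing a t-statistic (at 99 df, 1.875 is p = 0.064). The documents do not support a change. The 0.06 is 0.061 rounded, and simulated total two-sided error under the one-directional interim rule is 8.0–8.6% on every reading, below the stated 10%. Stricter t cut-offs would only cost about half a point of power.

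**Conclusion.** The 5% allowance is wrong for the boundary the plan specifies; about 11% is needed. The consequence is small: about 89% power instead of 90% at the plan's own 10% loss (88.3–88.6% with matched t cut-offs), and a loss tolerance of about 5–7% instead of 10%. This rests on d = 0.6, R-squared 0, one look at half the information, and 114 as the total enrolled without replacements.

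Stronger readings do not follow. The trial is not materially underpowered: 90% holds if about 106–108 are evaluable, and power is about 92% if all 114 are. Nor does the arithmetic require about 109 evaluable, since 98 already exceeds 90%. A figure of 88.5% can be reached by applying 5% to the exact 90% normal design, but that describes about 100 patients (95.1 × 1.05 = 99.9), not the 102 to 103 the plan would have. The boundary of 1.875, the fixed size of 98 and the type I error control all stand.

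**What to change.** In 9.2, keep 114 (57 per arm) and replace the derivation by percentages (15%, made up of 5% and 10%) with a statement along these lines:

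- The fixed design needs 98; the two-look Pocock design inflates the fixed-design size by about 11%.
- About 106–108 evaluable participants are needed for 90% power, allowing for the small surplus already in 98.
- At R-squared 0, 114 enrolled therefore gives 90% power with about 5–7% loss, about 89% with 10% loss, and about 92% with none.

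Do not simply change 5% to 11%, because with the 10% loss that implies about 120 enrolled. Leave the efficacy thresholds in 9.4.2 and 9.4.6 unchanged.

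The cost is wording in one section. No patients are added and no decision rule changes. The stated loss allowance becomes smaller, and the power quoted at 10% loss is about one point lower.

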9.3 POPULATIONS FOR ANALYSES

Intention-to-Treat Analysis Dataset: Participants will be analyzed based on their treatment assignment.

Per Protocol Analyses Dataset: All participants completing the study who complied with the protocol.

Safety Analysis Dataset: all study participants.

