1.3 SCHEDULE OF ACTIVITIES (SOA)

Procedures	Enrollment, Study Visit 1, Day 0	Study Visit 2 Day 2	Study Visit 3 Day 4	Study Visit 4 Day 6	Study Visit 5 Day 14+/- 2 days	Study Visit 6 Day 28+/- 2 days
Informed consent	X					
Demographics	X					
Medical history	X					
Randomization	X					
Administer study intervention: Subjects receive two days worth of drug/placebo on days 0, 2, 4 and one day of drug/placebo on day 6	X Drug/placebo For 2 days	X Drug/placebo For 2 days	X Drug/placebo For 2 days	X Drug/placebo For 1 day		
Nasopharyngeal swabs, saliva for COVID-19 RT-PCR and antigen testing	X	X Swabs optional	X	X Swabs optional	X	X
Physical exam: Vital signs, wt, pulse oximetry, other as clinically indicated	X	X	X	X	X	X
Urine pregnancy test (as indicated)	X					
Blood pregnancy test (as indicated)					X	
Hematology and coagulation	X				X	X
Blood chemistries	X				X	X
Adverse event review and evaluation	X	X	X	X	X	X
Concomitant medication review	X	X	X	X	X	X
Blood for research biorepository	X				X	X
Complete Case Report Forms (CRFs)	X	X	X	X	X	X

All subjects, regardless of study arm (blinded to subjects and investigators), will be tracked for their health status through daily phone calls from days 0 to day 14 with routine, scheduled daily phone calls by study staff to help participants fill out symptom scores on the standardized COVID-19-PRO instrument. Any subject reporting concerning symptoms, particularly chest pain, shortness of breath, extreme prostration, change in mental status will be referred to for emergency care. Subjects will be given a contact phone number of PI or designee to contact for any concerns. If there is complete resolution of symptoms at the day 14 visit, then phone calls will not be routinely continued by our study staff but subjects will be encouraged to call PI or designee for concerns or discussions.

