4 STUDY DESIGN

4.1 OVERALL DESIGN

*The scientific integrity of the trial and the credibility of the data from the trial depend substantially on the trial design. A description of the trial design should be consistent with the **Protocol Synopsis (section 1.1)** and **Protocol Schema (section 1.2)** and include:*

Hypothesis: Camostat mesylate, a serine protease inhibitor shown to inhibit SARS-CoV-2 replication *in vitro* and to reduce mortality in a mouse model of SARS, inhibits SARS-CoV-2 replication in early stage, laboratory-confirmed, ambulatory COVID-19 patients.

Trial phase: This is a phase II trial of camostat mesylate, a drug approved for clinical use in Japan for treatment of pancreatitis and postoperative reflux esophagitis.

Trial design: Randomized, double-blind, placebo-controlled clinical trial

Methods to minimize bias: Participants will be randomized equally to camostat mesylate or identical appearing placebo using a permuted-block design with variable block size. Actual treatment assignment will be concealed from the investigators and the participants.

Number of study groups/arms and study intervention duration: Two arms: **Group A, study drug (camostat mesylate); Group B, placebo.** **Duration of study: 7 days.** **Duration of involvement by participants: 28 days.**

Number of Sites: one

Name of study intervention: Camostat mesylate

Stratification: None

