4.4 END OF STUDY DEFINITION

A participant is considered to have completed the study if he or she has completed all phases of the study including the last visit or the last scheduled procedure shown in the Schedule of Activities (SoA), Section 1.3. The end of the study is defined as completion of the last visit or procedure shown in the SoA in the trial globally.

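### The per-protocol set requires completion of the day-28 visit, so the secondary per-protocol analysis of the day-4 endpoint drops participants with valid primary data because of later events

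*Combined protocol and SAP*

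**What the plan says.** Section 9.3 defines the per-protocol dataset once, for all endpoints: "All participants completing the study who complied with the protocol".

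Section 4.4 says what completion means: "A participant is considered to have completed the study if he or she has completed all phases of the study including the last visit"; a final scheduled procedure is named as the alternative. In section 1.3 the last column of the Schedule of Activities is "Study Visit 6 Day 28+/- 2 days", and section 4.1 agrees: "Duration of involvement by participants: 28 days".

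The primary hypothesis in section 9.1 concerns the "change from baseline to day 4 in respiratory (Nasopharyngeal swab, saliva RT-PCR") log10 viral load. Section 9.4.2 states: "The primary analysis will be according to intent-to-treat and conducted using ANCOVA". It then adds, for the same endpoint: "We will also conduct a per-protocol analysis as a secondary analysis".

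No section gives a per-protocol rule for a particular endpoint, and none keeps in the set a participant who leaves after day 4.

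**The concern.** A per-protocol analysis of a day-4 endpoint is meant to show the effect in participants who took the assigned treatment as planned up to day 4. Here, membership also depends on what happens over the following 24 days. The day-4 value is already recorded by then, so the extra condition adds nothing to the estimate.

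It has two costs. Valid observations are discarded, which lowers precision. More importantly, the set is selected on events after the endpoint, and some of these may be linked to treatment or disease course. Sections 7.1 and 7.2 list adverse events and disease progression among the reasons for stopping or withdrawal, and section 7.3 covers loss to follow-up. Section 3 itself expects viral load to relate to disease severity, so late loss could be related to the day-4 outcome. If the per-protocol and intention-to-treat results then differed, a reader could not tell an adherence effect from late attrition.

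**Working it through.** **Reading the text.** Three sections settle the point together: 9.3 requires completion, 4.4 defines it by the last scheduled visit, and 1.3 places that visit at day 28. Section 4.1 also gives a seven-day study duration, but 4.4 is the explicit definition of completion, and day 7 is still later than day 4. The second condition in 9.3, compliance, has no criteria. Section 6.4 makes nasopharyngeal swabs mandatory at days 14 and 28, so a missed late swab could also exclude someone whose primary data are complete.

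**The plan's own figure.** The inputs in section 9.2 are changes of 4 and 1 (difference 3), SD 5.0, two-sided alpha 0.10, power 90% and R-squared 0. The standardised difference is 3/5 = 0.6, which is 0.3 on the scale of SD of means over SD. Noncentral-t power for ANCOVA with one covariate is 0.8985 at 48 per arm and 0.9038 at 49 per arm, so 49 per arm (98 in total) reproduces. Inflation gives 98 × 1.15 = 112.7, or 56.35 per arm, rounded up to 57 per arm and 114 in total. The change proposed here alters none of these figures.

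**Precision.** Let L be the proportion of otherwise eligible per-protocol participants lost between day 4 and day 28, equal in both arms. The standard error is proportional to 1/√n, so it is multiplied by 1/√(1 − L). The documents do not give L, so the values below are assumptions. Power is for a difference of 0.6 SD, starting from 114 analysable participants with no replacement.

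| Assumed L | Remaining of 114 | SE multiplier | Power, alpha 0.10 | Power, alpha 0.06 |
|---|---|---|---|---|
| 0% | 114 | 1.000 | 93.8% | 90.3% |
| 5% | about 108 | 1/√0.95 = 1.026 | 92.7% | 88.8% |
| 10% | about 103 | 1/√0.90 = 1.054 | 91.5% | 87.1% |
| 20% | about 91 | 1/√0.80 = 1.118 | 88.5% | 83.0% |

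The 0.06 column uses the final-look level that section 9.4.2 sets for the primary outcome. The plan sets no separate level for the per-protocol analysis.

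**Selection.** This is an illustration by simulation, and every input is assumed. There is no true effect, the day-4 outcome is in SD units, and the log-odds of late loss rise by 0.7 to 1.5 per SD of worse day-4 viral load.

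| Late loss, one arm vs the other | Spurious difference (SD) |
|---|---|
| 10% vs 10% | about 0 |
| 5% vs 15% | 0.06 to 0.11 |
| 10% vs 20% | 0.06 to 0.11 |
| about 0% vs 20% | 0.13 to 0.23 |

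The arm with more late loss looks better, because its worse outcomes are removed. Against the planned 0.6 SD, 0.11 is about 18% and 0.23 about 38%. When late loss does not depend on the day-4 outcome, the simulated difference is zero to within 0.001 SD.

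**The case against.** The strongest case on the other side is that little depends on this. The primary analysis is by intention to treat, and the per-protocol analysis is expressly secondary. No sample size, alpha, boundary or stopping rule uses it. That stands, and it limits the importance of the point.

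Three stronger readings are tempting, and the documents do not support them.

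- A reader might infer that the 10% in section 9.2 is the share of valid participants who would be dropped. It is an allowance for loss within a sample-size calculation for the day-4 outcome. It is not a loss rate from day 4 to day 28. The 5.4% figure is therefore one value in an assumed range, not a consequence of the plan.
- A reader might infer that anyone hospitalised after day 4 is excluded. No section says so. Section 7.2 lets an investigator withdraw a participant for disease progression but does not require it, and section 7.3 plans attempted follow-up of those hospitalised outside the health system. Hospitalisation excludes someone only if it leads to withdrawal or to missed required visits.
- A reader might take the precision loss as a net shortfall. Section 7.2 says treated participants who later withdraw or are withdrawn will be replaced, and section 7.3 counts those lost to follow-up as withdrawn. Replacement offsets part of the loss in numbers. It does not undo the selection, because those who leave are still dropped from the set.

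It is also fair to say that bias is not shown, since equal rates and an equal mechanism give about none. The missing-data sensitivity analyses in section 9.4.2 are not stated to apply to the per-protocol set, so they do not answer the point.

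**Conclusion.** The point holds as a defect in a stated rule: the per-protocol definition in 9.3, read with 4.4 and 1.3, discards valid day-4 data because of later events. Its reach is limited to the secondary per-protocol analysis.

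The precision cost is modest. For assumed late loss of 5% to 20%, the standard error rises by about 2.6% to 11.8%, before any replacement. Selection matters more, but its size and direction cannot be derived from the documents. It requires late loss that both differs by arm and is related to day-4 viral load. The simulated values rest wholly on assumed rates and slopes, and they should not be read as a forecast for this trial.

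**What to change.** In section 9.3, remove the completion requirement and define per-protocol membership separately for each endpoint, by events up to that endpoint's time point only. For the primary endpoint the set would be participants who:

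- were eligible;
- complied with assigned treatment through day 4, judged by the dosing assessment already collected under section 6.4;
- have valid day-0 and day-4 samples of the specimen type being analysed (nasopharyngeal swab or saliva).

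Later endpoints would use the same form with their own time points. The team should write down what counts as compliance, since 9.3 gives no criteria and section 6.4 provides only a verbal assessment. All of this should be fixed before unblinding, so that membership is not decided with knowledge of assignment.

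The revised set still conditions on compliance after randomisation up to day 4, as any per-protocol set does, so it narrows selection without removing it. The cost is a short rewording of 9.3 and one decision on the compliance criterion. It needs no new data, visits or participants. This is a free improvement, desirable rather than essential.
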